4.7 Participant Treatment

At baseline, participants will be given ivermectin (150 $\mu\text{g}/\text{kg}$) pretreatment. This pretreatment will be provided the participants' villages near their homes following their consenting to participate in the study. *Please note, *all participants* will be treated with ivermectin at baseline to ensure that they have low skin and ocular Mf counts at the time of enrollment. (This treatment is *in addition to* the pretreatment with ivermectin given in the Part I study).

After the baseline treatment with ivermectin alone, participants will be randomly assigned to one of the following treatment arms (all oral medications)*:

I. Ivermectin 150 $\mu\text{g}/\text{kg}$ plus albendazole (400 mg)

II. IDA single oral dose

- a. Ivermectin, 150 $\mu\text{g}/\text{kg}$

- b. Diethylcarbamazine citrate, 6 mg/kg
- c. Albendazole, 400 mg

III. IDA three one time daily oral doses

- a. Ivermectin, 150 μ g/kg
- b. Diethylcarbamazine citrate, 6 mg/kg
- c. Albendazole, 400 mg

Randomized treatment to one of the three treatment arms will occur in cohorts of up to 20 individuals. This is based on the project's capacity for transport, examination, and housing of participants. Initial participants will be individuals who had zero Mf in the eyes six months after pre-treatment with IVM in Part I and zero Mf in the eyes at baseline for Part II. If IDA proves safe in all of these participants,(i.e. if there are no serious or severe adverse events in *any* participant in the first 7 days) the study will continue with participants who had Mf in the anterior chamber in either eye six months after IVM pre-treatment in the Part I study or at the baseline exams for this study. Study investigators will monitor the safety of the participants in each treatment cohort for 7 days before dosing the next cohort, and they will suspend the study if any treatment-related serious or severe adverse events occur. If SAEs are reported, the DSMB will be asked to review the cases and to implement study stopping and pausing guidelines if the SAEs are found to be related to study treatments.

4.7.1 Plan for Re-dosing

Participants who vomit within 30 minutes after dosing will be redosed the same day at least two hours after the first attempt. If they vomit the second dose, they will be excluded from the study and provided treatment with ivermectin alone the next day.

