5.2 Risk of ocular exams

The ophthalmological procedures are routine and associated with minimal risk. The possible risks are related to the ocular medications administered during these tests. To perform applanation tonometry and slit lamp examinations investigators will apply local anesthetic eye drops approved for use in Ghana (e.g. lidocaine, proparacaine or tetracaine), which may cause mild local reactions such as conjunctival hyperemia and ocular irritation/burning.

To perform indirect ophthalmoscopy, retinal photography and OCT, investigators will apply eye drops to dilate the pupil (e.g. generic tropicamide) which may cause transient blurred vision, photophobia, ocular stinging. These eye drops are routinely used in persons undergoing ophthalmology examinations. Dilating eye drops will only need to be applied once, and the pupils will remain dilated for the remainder of the examination. Rare adverse events include increases in intraocular pressure and superficial punctate keratitis; other uncommon systemic side effects include xerostomia, tachycardia, headache, nausea and vomiting.

5.3 Risk of study medications:

The combinations of IVM plus albendazole or DEC plus albendazole are widely used in MDA programs. There have also been 3 clinical trials and extensive safety trials of IDA in 5 countries. A published study demonstrated no significant interactions between the three IDA drugs³⁵. The WHO has recently recommended use of IDA for LF elimination programs in areas without co-endemic onchocerciasis or loiasis that are not currently on track to meet the 2020 deadline (http://www.who.int/neglected_diseases/news/WHO_recommends_triple_medicine_therapy_for_LF_elimination/en/). Potential risks for each drug separately, with some indication of how likely these are to occur, are summarized below.

Risks of Diethylcarbamazine (DEC): This drug is known to be safe for treatment of LF and hundreds of millions of people are treated each year by MDA programs in areas without coendemic onchocerciasis or loiasis. Mild to moderate adverse events are seen in persons with microfilaremia. The most adverse events are headache, fever, joint pain, unusual tiredness or weakness. Less common are dizziness, nausea or vomiting. Persons with onchocerciasis often experience pruitis and dermal edema. Ocular AEs in onchocerciasis patients that have not received a clearing dose of IVM are described above (see *Background*).

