Note that the samples sizes per treatment group in this study are not sufficient to provide a robust safety profile (e.g., high confidence that the rate of SAEs after treatment is less than 0.1%). This proof of concept study will allow for initial safety assessments to be performed. Additional, larger studies will be required to establish a more complete safety profile. The safety assessments put in place for this study along with the frequent and ongoing review by the DSMB will provide a strong foundation to evaluate the participant's safety throughout the study.

Data from all participants in this study will be analyzed for safety and efficacy outcomes. The study population for the primary and secondary endpoints related to adult worm viability and fertility are persons who were enrolled and who have nodulectomies performed 18 months after treatment. The study population for secondary efficacy outcomes related to microfilariae in the skin are participants who were enrolled in the study who have follow-up microfilaria testing by skin snip examination at time points (12, 18 months) as indicated in the diagram on page 26 of the protocol. The study population for the early (7 day) safety analysis are participants who receive the study drugs who have safety assessments during the 7 days after dosing. A separate safety analysis will consider data from the follow-up examinations conducted 3 months after dosing.

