11.5 Withdrawal

Entry into the study and participation will be strictly voluntary. It will be made clear that refusal to participate or a decision to withdraw can occur at any time throughout the course of the study and will not influence their rights or the care they receive at local health facilities.

In two of the three treatment arms the participants receive a single treatment. In the 3rd treatment arm the patients receive treatment on three consecutive days. While there is no dose titration in place the investigator has the discretion to discontinue treatment if the treatment appears to be creating distress to the participant. The study investigator would monitor these participants closely and assess any adverse events that have occurred. There is no plan in place for the study investigator to re-initiate treatment once it has been discontinued.

Withdrawal from the study can be at the participant or investigator discretion at any time during the trial. All subjects that withdraw from the study will be encouraged to complete the safety follow-up visits (daily for 7 days after dosing and at 3 months).

Data collected on the participant up to the point of withdrawal remains part of the study database. If the participant withdraws from the interventional part of the study and agrees to continue being seen for the safety follow-up visits the associated clinical outcome information such as medical information and laboratory results will be part of the study database.

There is no plan to replace withdrawn participants.

Protocol deviations are collected through the electronic data capture system (i.e. visits out of window, in-appropriate dosing, etc.) and reviewed through the tables, figures, listings. Additionally, a Protocol Deviation Log has been put in place to address deviations not picked up by EDC. Participants who fail to report for follow-up examinations will not be considered to have withdrawn, and the study team will attempt to contact them for follow-up testing at later time points listed in the protocol.

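### Vomiting a repeat dose removes a randomised participant from the study, and nothing in the plan keeps that person in the 12- and 18-month efficacy follow-up

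*Combined protocol and SAP*

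**What the plan says.** **The rule (section 4.7.1).** "Participants who vomit within 30 minutes after dosing will be redosed the same day at least two hours after the first attempt". Then: "If they vomit the second dose, they will be excluded from the study and provided treatment with ivermectin alone the next day". The text refers to dosing in general and does not mention a particular dosing day.

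**Its timing (section 4.7).** "After the baseline treatment with ivermectin alone, participants will be randomly assigned to one of the following treatment arms". The rule therefore acts on people who have already been randomised and dosed.

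**Number of dosing days (section 11.5).** Of IVM/ALB and single-dose IDA, the plan says: "In two of the three treatment arms the participants receive a single treatment". Of the remaining IDA arm, it says: "In the 3rd treatment arm the patients receive treatment on three consecutive days".

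**Vomiting as a drug effect (section 5.3).** For DEC: "Less common are dizziness, nausea or vomiting". Vomiting is also listed for albendazole. DEC is given only in the two IDA arms; albendazole is given in all three.

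**Who is analysed (section 8.2).** "Data from all participants in this study will be analyzed for safety and efficacy outcomes". The same paragraph then narrows this by endpoint. The worm endpoints use enrolled people with a nodulectomy at 18 months. The skin endpoints use those with follow-up snips. The early safety analysis uses those who took study drug and were assessed in the following 7 days.

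**What happens after withdrawal (section 11.5).** "All subjects that withdraw from the study will be encouraged to complete the safety follow-up visits", meaning the 7 daily checks and the 3-month visit. Data collected before withdrawal are kept. A person who leaves only the interventional part and agrees to safety visits continues to contribute clinical data. Withdrawn participants are not replaced.

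**The concern.** An exclusion that happens after randomisation, and whose trigger is a known effect of the drugs being compared, selects participants on tolerability. The groups left at 18 months are then no longer the groups that were randomised.

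The plan contains no provision that would prevent this. Section 11.5 asks withdrawn people back for safety visits only, and it does not say that someone excluded under 4.7.1 counts as withdrawn. Without an 18-month nodulectomy the person is outside the primary efficacy population by definition. The same holds for the skin endpoints without the later snips.

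What is at stake is the randomised comparison on worm fertility and skin microfilariae, above all for the three-day IDA arm. That arm may have three occasions for the event, and a person could be excluded after one or two complete daily doses. The ivermectin given the next day is a further antifilarial treatment, and the plan does not say how the analysis should treat it.

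**Working it through.** **1. The plan's own figures (section 8.1).** Inputs: fertile-worm rates of 30% (IVM/ALB), 15% (IDA1) and 10% (IDA3), 6 female worms per person, ICC 0.30, two-sided 0.05, 80% power.

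- Design effect: 1 + 0.30 × (6 − 1) = 2.5.
- Worms per group, pooled two-proportion formula without continuity correction: 121 for 30% versus 15%, and 62 for 30% versus 10%.
- Subjects: 121 × 2.5 / 6 = 50.4, so 51; 62 × 2.5 / 6 = 25.8, so 26. Both match the plan.
- The planned enrolment of at least 61 per arm is used below.

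**2. Exclusion risk by arm.** Let q be the probability, on one dosing day, of vomiting the dose and then the repeat dose. The documents give no value, so 0.2% to 3% is assumed. A one-day arm has risk q. If the rule applies on every dosing day, with equal and independent daily risk, the three-day arm has risk 1 − (1 − q)³.

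**3. Possible bias.** Suppose, as an illustration, that excluded IDA3 participants had the control rate of 30% fertile worms and the others 10%. The all-randomised IDA3 rate is then 10% + 20% × [1 − (1 − q)³], against 10% as analysed.

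| q | One-day arm: risk (of 61) | Three-day arm: risk (of 61) | Ratio | IDA3 fertile rate, all randomised |
|---|---|---|---|---|
| 0.2% | 0.2% (0.1) | 0.6% (0.4) | 2.99 | 10.1% |
| 0.5% | 0.5% (0.3) | 1.5% (0.9) | 2.99 | 10.3% |
| 1% | 1.0% (0.6) | 3.0% (1.8) | 2.97 | 10.6% |
| 2% | 2.0% (1.2) | 5.9% (3.6) | 2.94 | 11.2% |
| 3% | 3.0% (1.8) | 8.7% (5.3) | 2.91 | 11.7% |

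On these assumptions the selection flatters IDA3 by 0.1 to 1.7 percentage points, against an assumed contrast of 20 points.

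**4. Power.** With an effective number of worms of subjects × 6 / 2.5, IVM/ALB versus IDA1 has 80.6% power at 51 per group. Removing q from both arms gives 80.2% at q = 1% and 79.8% at q = 2%. IVM/ALB versus IDA3, starting from 51 per group, keeps about 97% at either value.

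**5. Follow-up, section by section.**

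| Follow-up | Secured for someone excluded under 4.7.1? |
|---|---|
| 7-day adverse events | Largely. Participants stay at the centre with daily checks (4.6, 7.2), and the 8.2 safety population turns on drug received and assessments made |
| 3-month safety visit | Only if the exclusion counts as a withdrawal under 11.5, and then encouraged rather than scheduled |
| 12- and 18-month skin snips | No provision |
| 18-month nodulectomy | No provision |

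**The case against.** Several stronger readings are tempting, and the documents do not support them.

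- **The worst tolerators vanish from the safety results.** A reader might infer this from the word excluded. But such a person has received study drug, is housed at the centre under daily assessment, and meets the 8.2 definition of the 7-day safety population. Section 11.5 keeps the data already collected. What remains is narrower: 11.5 does not say whether an exclusion under 4.7.1 is a withdrawal.
- **The three-to-one imbalance undermines the primary comparison.** Section 8.1 names IVM/ALB versus IDA1 as primary, and each of those arms has one dosing day. Only a DEC-related difference in vomiting could unbalance exclusions there. The imbalance in dosing days concerns IVM/ALB versus IDA3.
- **The sections contradict each other outright.** The general statement in 8.2 about analysing all participants is followed directly by endpoint-specific populations. The sections can be read together: no nodulectomy, so not in the worm analysis. The fault is that the plan leaves the status of these people unstated and lets them fall out by default.
- **The threefold ratio is a fact of the design.** It is an upper figure. Section 4.7.1 does not say that it applies on each day. If some people are consistently prone to vomiting, they leave on day 1 and the ratio falls below three.

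The size is also open to challenge. The event needs two episodes of vomiting on one day, the first within 30 minutes. At 0.2% to 0.5% per dosing day it affects fewer than one person of 61 in any arm, far below the 20% drop-out allowance. That stands as a limit on magnitude. It does not remove the problem, because ordinary drop-out is not prescribed by the protocol in response to a drug effect.

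**Conclusion.** The point holds for the efficacy follow-up. Section 4.7.1 prescribes a post-randomisation exclusion triggered by a listed drug effect, and no section brings these participants back for the 12- and 18-month assessments. The safety counts are mostly covered, subject to the unresolved link between 4.7.1 and 11.5.

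The size is modest: 0.1 to 1.8 people of 61 in a one-day arm and 0.4 to 5.3 in the three-day arm. This rests on an assumed rate of 0.2% to 3% per dosing day, on the rule applying each day, and on equal, independent daily risk. The shift in the IDA3 fertility rate further assumes that excluded people would have had the control rate. Power is hardly affected. The change is still worth making, because it is cheap and because 18-month nodule data not collected from these people may not be recoverable later.

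**What to change.** Reconcile sections 4.7.1, 8.2 and 11.5 so that stopping randomised treatment is distinct from leaving the study. The re-dosing and next-day ivermectin provisions are left as written; no view is taken on them here. The plan should state that:

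1. these participants are offered, subject to consent, the safety, skin-snip and 18-month visits already scheduled, including nodulectomy;
2. they are analysed in the arm to which they were randomised, and are included in the safety set;
3. the next-day ivermectin is disregarded in the as-randomised analysis, so that outcomes are used regardless of it (a treatment-policy approach);
4. their number is reported by arm and by dosing day;
5. a supportive analysis omits them.

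Section 4.7.1 should also say whether it applies on every dosing day, and 11.5 whether such a case is a withdrawal.

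The cost is a wording change before dosing begins, follow-up visits for a handful of people at most, and a slight dilution of the efficacy contrast, since people who did not complete their assigned regimen are counted in it.

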4.7.2 Concomitant Medications

Participants will be told to continue to take their regular medications. Additionally, each participant will be instructed and provided a study ID card during consenting that indicates that they are participants in a clinical trial and should not take ivermectin/Mectizan MDA given by mass drug administration (MDA) program or other groups until nodulectomies have been performed at 18 months.. Each participant will be instructed and provided a study ID card during consenting that indicates that they are participants in a clinical trial and should not take ivermectin (or Mectizan) provided by a government program or other group until nodulectomies have been performed 18 months after the Part II treatment.

4.8 Assessment of Adult Filarial Worms

Some of the primary and some secondary efficacy endpoints for this will be based on histology results from examination of nodules collected from participants at the end of the study. Nodulectomies will be performed at UHAS School of Public Health Research Centre in Hohoe. The nodules will be preserved before being sent to a histology laboratory (location to be decided) for embedding, slide preparation, and histological staining. This will include H&E for general morphology, APR-immunostain for differentiating dead and live worms⁴³, and Gomori iron stain for

worm age assessment. The stained nodule sections will be read by two independent readers. The readers will not have access to each other's results until after they have entered their results. The two results will be compared, and the two readers will work together to reconcile any discrepancies. A third reader can be used to reconcile discrepancies if the two readers cannot agree. The reconciled result will be considered to be the final result.

4.9 Study Duration and Timeline

Participants will be followed for 18 months after treatment. Participants will be transported to the study site at the University of Health and Allied Sciences (UHAS) School of Public Health Research Centre in Hohoe, Ghana to complete enrollment and treatment procedures and for assessment of adverse events. Participants will be housed at a clinical facility on the municipal hospital grounds for 7 days after treatment. Participants will be brought back to the clinical research facility in Hohoe 3 months after treatment for 2 days in order to complete ocular re-examinations and skin snip testing. Skin snips will be collected 12 months after treatment in the participants' home village. The final visit will occur at 18 months \pm 60 days when participants are once again brought to the clinical facility in Hohoe for 2 days to have skin snip testing and nodulectomies.

The on-study period per participant is approximately 20 months and it is anticipated that the duration of the study will be up to 24 months, including 4 months for recruitment.

[figure not shown]

Figure 1. Study overview. Part I examines the kinetics of clearance of Mf from skin and eye following IVM treatment as well as Mazzotti reactions and ocular safety of IVM for treatment of onchocerciasis (now in progress). Part II examines the safety and efficacy of IDA (current protocol). Participants will be recruited from the Part I study into the Part II study, and given a second pre-treatment dose of ivermectin, skin snip and eye examinations will be conducted prior to randomization and dosing with the investigational combination therapies.

The following tolerances will be allowed for flexibility in scheduling participant visits:

- Day 7 visit \pm 1 day
- Month 3 visit \pm 14 days

- Month 12 visits \pm 30 days
- Month 18 visit \pm 60 days

4.10 Investigational Product Supply and Storage

Drugs used for this protocol will be purchased from manufacturers who donate their product for use in the Global Program to Eliminate Lymphatic Filariasis. Alternatively, WHO approved generic versions may be purchased. If necessary, import approvals will be requested from the government of Ghana.

Albendazole and IVM are approved for use and widely used in Ghana for lymphatic filariasis and/or onchocerciasis control and elimination. However, DEC is not approved for use in people with lymphatic filariasis or onchocerciasis. Thus use of DEC in this study will require approval by ethical review committees and by the Ghana FDA.

Detailed information for each drug is available from the manufacturers and the package inserts are included in an appendix to this protocol (Appendix B).

Investigational products should be stored in a secure, locked pharmacy room. In this study all drugs will be stored at no greater than 30°C per the package insert. Documentation of temperature logs will be done per the study site SOPs.

5 POTENTIAL RISKS AND BENEFITS

5.1 Risks of Skin Snips:

This procedure is associated with a small risk of bleeding and infection. The skin will be disinfected before a snip is taken with a sterile scleral punch. The snip (about 2 mg) will cause a superficial wound of the skin at the iliac crests and calves, which will be covered with a plaster for one day. These procedures are routine and designed to minimize risks of infection or bleeding. The scar will be 2 mm or less in size.

5.2 Risk of ocular exams

The ophthalmological procedures are routine and associated with minimal risk. The possible risks are related to the ocular medications administered during these tests. To perform applanation tonometry and slit lamp examinations investigators will apply local anesthetic eye drops approved for use in Ghana (e.g. lidocaine, proparacaine or tetracaine), which may cause mild local reactions such as conjunctival hyperemia and ocular irritation/burning.

To perform indirect ophthalmoscopy, retinal photography and OCT, investigators will apply eye drops to dilate the pupil (e.g. generic tropicamide) which may cause transient blurred vision, photophobia, ocular stinging. These eye drops are routinely used in persons undergoing ophthalmology examinations. Dilating eye drops will only need to be applied once, and the pupils will remain dilated for the remainder of the examination. Rare adverse events include increases in intraocular pressure and superficial punctate keratitis; other uncommon systemic side effects include xerostomia, tachycardia, headache, nausea and vomiting.

5.3 Risk of study medications:

The combinations of IVM plus albendazole or DEC plus albendazole are widely used in MDA programs. There have also been 3 clinical trials and extensive safety trials of IDA in 5 countries. A published study demonstrated no significant interactions between the three IDA drugs³⁵. The WHO has recently recommended use of IDA for LF elimination programs in areas without co-endemic onchocerciasis or loiasis that are not currently on track to meet the 2020 deadline (http://www.who.int/neglected_diseases/news/WHO_recommends_triple_medicine_therapy_for_LF_elimination/en/). Potential risks for each drug separately, with some indication of how likely these are to occur, are summarized below.

Risks of Diethylcarbamazine (DEC): This drug is known to be safe for treatment of LF and hundreds of millions of people are treated each year by MDA programs in areas without coendemic onchocerciasis or loiasis. Mild to moderate adverse events are seen in persons with microfilaremia. The most adverse events are headache, fever, joint pain, unusual tiredness or weakness. Less common are dizziness, nausea or vomiting. Persons with onchocerciasis often experience pruitis and dermal edema. Ocular AEs in onchocerciasis patients that have not received a clearing dose of IVM are described above (see *Background*).

Risks of Albendazole (ALB): This medication is safe and is provided as MDA to hundreds of millions of persons in Africa each year by programs to eliminate LF and onchocerciasis and to children in school-based deworming programs. Headache, nausea, stomach pain and/or vomiting sometimes occur after treatment, and this tends to be more common in persons with heavy STH infections. Severe allergic reactions occur rarely, and these can include rash, hives, itching, difficulty breathing, tightness in the chest, swelling of the mouth, face, lips, or tongue. Stevens-Johnson syndrome has been reported, but this is very rare. Mild, transient elevation in liver transaminases rarely occurs after single dose ALB treatment. More severe liver toxicity and leukopenia sometimes occur in persons treated with long courses of ALB with doses of 800 mg per day or more.

Risks of Ivermectin (IVM): This medication is safe and is provided as MDA to more than 100 million persons in Africa each year by programs to eliminate LF and onchocerciasis. The most common side effects are diarrhea, dizziness and nausea. Persons with onchocerciasis sometimes experience rash, hives, itching (see Mazzotti reactions, below), difficulty breathing, tightness in the chest, swelling of the mouth, face, lips, or tongue; eye pain, swelling, or redness. Seizures, fainting, mild decrease in leukocyte counts, elevated liver function tests, and cardiovascular effects that included tachycardia and orthostatic hypotension have been reported, but these adverse events are rare and not necessarily related to IVM treatment.

Mazzotti Reactions: These AEs are caused by inflammatory and immune reactions to microfilariae that are killed by IVM or DEC as described above. Mazzotti reactions need to be differentiated from any coincidental illnesses that may occur in temporal relationship with IVM treatment. Common systemic clinical manifestations of the Mazzotti reaction include pruritus, rash, lymphadenitis, headache, myalgia, arthralgia, hypotension, fever, and swelling of the face and limbs. Ocular events include epiphora, photophobia, and conjunctival injection. The factors that govern the Mazzotti reaction include the intensity of infection, the dose regimen, and the microfilaricide used. These reactions usually resolve spontaneously, although treatment with ordinary analgesics (e.g. acetaminophen; aspirin,

ibuprofen) and antihistamines (e.g. diphenhydramine) are often provided in clinical trials. Most AEs resolve within 3- 4 days after treatment.

The DEC is manufactured by Pfizer and will purchased through Amtrex Enterprises. Ivermectin and albendazole will be obtained from Merck and GlaxoSmithKline respectively. Each drug purchased, will have certificates of analysis which will be retained in the study trial master files and will be provided to the Ghana Health Service and FDA if required.

